5.2 Exclusion Criteria

- Do Not Resuscitate (DNR),
- Comfort Care and end-of-life patients
- Patients with SOFA score greater than 12
- Pregnant women
- Jehovah witnesses that do not accept albumin.
- Active bleeding (e.g., gastrointestinal bleeding)
- Acute neurological syndromes (e.g., stroke, hemorrhage, etc)
- End-stage Renal Disease (ESRD)
- Transaminitis

- Renal replacement therapy
- Chronic Liver Disease
 - Childs-Pugh Class C or
 - Diagnosis of Cirrhosis
- Heart rate less than 50 bpm,
- Respiratory rate less than 8 rpm,
- Temperature less than 95°F or 35°C
- Tumor Lysis Syndrome
- Myasthenia gravis
- Sulfite Allergy: amino acids administration are contraindicated. It is more common in steroid dependent asthmatics. (Please note that this is NOT sulfa allergy and is NOT contraindicated patients with sulfa allergy). Sulfites are present in dried fruits, beer, wines, sausages, jams, maple syrup, and many other food products.
- Serum sodium concentration < 130 mEq/L or >150 mEq/L (Note: Once serum sodium levels are \geq 130 or \leq 150 mEq/L within 12 hours after meeting inclusion criteria, the patient can then be considered for the study. This is only a temporary restriction).
- Serum Creatinine level: SCr \geq 3 mg/dL (Note: Once serum creatinine levels are \leq 2.5 mg/dL within 12 hours after meeting inclusion criteria, the patient can then be considered for the study. This is only a temporary restriction).
- Urine output < 400 cc/24hrs (Note: Once urine output levels are \geq 400 cc within 12 hours after meeting inclusion criteria, the patient can then be considered for the study. This is only a temporary restriction).
- Hyperkalemia K > 5.5 mEq/L (Note: Once potassium levels are \leq 5.5 mEq/L within 12 hours after meeting inclusion criteria, the patient can then be considered for the study. This is only a temporary restriction).
- Hyperglycemia: Glucose > 250 mg/dL (Note: Once glucose is below 250 mg/dL within 12 hours after meeting inclusion criteria, the patient can then be considered for the study. This is only a temporary restriction.)

- Hypophosphatemia: Serum Phosphorous < 1.5 mg/dL (Note: Once phosphorus is above 1.5 mg/dL within 12 hours after meeting inclusion criteria, the patient can then be considered for the study. This is only a temporary restriction.)

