 - a. Time from hospital admission to admission to the ICU (Length of stay before admission to the ICU)
 - b. Length of the stay in the ICU
 - c. Length of hospital stay
- 2. Mortality
 - a. Hospital mortality
 - b. ICU mortality
 - c. 28 day mortality
 - d. 90 day mortality
- 3. Ventilator days – ventilator free days, duration of intubation (days)
- 4. Any newly documented hospital acquired infection(s)
- 5. Any acute kidney injury as defined by acute kidney injury network criteria:
 - a. An acute (within 48h) rise in serum creatinine of 0.3g/dl or more

- b. A percentage increase of serum creatinine of 50% or more
 - c. Documented oliguria <0.5 ml/kg/hr for >6 hours
 - d. Need for dialysis
 - e. Dialysis free days
- 6. Inotropic free days and duration of inotropic support (hours or days)
- 7. Vital signs and any hemodynamic monitoring (cardiac index, CVP, ScvO2) implemented will be recorded – there is no specific requirement for hemodynamic monitoring beyond arterial-line recorded MAP/BP/HR.
- 8. All patients will be followed up for up to 90 days.

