10.0 STATISTICAL CONSIDERATIONS

10.1 Study Endpoint and Outcomes

The primary objective of this study is to assess the efficacy of administering Early Metabolic Resuscitation with Standard of Care (SC + EMR) in patients diagnosed with septic shock for reducing 28 day mortality versus using the Standard of Care alone (SC).

The primary endpoint of the study is 28-day mortality. The rationale for selecting the 28-day timeframe as the primary endpoint for comparison is that the MDACC ICU length of stay and the hospital length of stay in patients diagnosed with septic shock have wide variability (ICU LOS = Mean 9.45 ± 13.06 min: 0 max: 104, and Hospital LOS = Mean $26.4 \pm SD 26.4$ min:1, max: 242). This variability is incurred from sources that cannot be controlled. For this reason, measures such as 28-day and 90-day mortality provide more objectivity and align with outcomes described in the literature.

Secondary outcomes include ICU mortality, hospital mortality, 90-day mortality, incidence of acute kidney injury (dichotomous variable), time on cardiovascular support (continuous variable), time on ventilator (continuous variable) and length of ICU and hospital stays (continuous variables).

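### The creatinine criterion for acute kidney injury is in the wrong unit (0.3 g/dl is 300 mg/dl), and the definition sets no baseline or start time although entry admits patients already below its oliguria threshold

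*Combined protocol and SAP*

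**What the plan says.** Section 7.2 (Outcome data, item 5) introduces the outcome as "Any acute kidney injury as defined by acute kidney injury network criteria" and lists:

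- 5a: "An acute (within 48h) rise in serum creatinine of 0.3g/dl or more"
- 5b: "A percentage increase of serum creatinine of 50% or more"
- 5c: "Documented oliguria <0.5 ml/kg/hr for >6 hours"
- 5d and 5e: need for dialysis, and dialysis-free days.

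Item 5 names no reference creatinine, gives no start for the observation window and has no rule for AKI already present. Item 4, directly above it, does carry such a limit: "Any newly documented hospital acquired infection(s".

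Section 10.1 lists the outcome as "incidence of acute kidney injury (dichotomous variable"), and AKI is the first complication named in secondary objective 3 (section 1.2).

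Section 5.2 excludes "Urine output < 400 cc/24hrs", but treats this as temporary. Once output reaches 400 "cc within 12 hours after meeting inclusion criteria, the patient can then be considered for the study". The same section excludes creatinine of 3 mg/dL or more, end-stage renal disease and renal replacement therapy. It does not exclude AKI by criteria 5a to 5c.

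**The concern.** There are two separate faults in the only operational definition of a named secondary outcome.

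The first is the unit. A threshold in g/dl makes criterion 5a impossible to meet. Applied literally, by a chart abstractor or in a program, it scores no events.

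The second is the missing baseline. The urine output limit for entry is an absolute volume, and the outcome threshold is a rate per kilogram. For nearly any adult weight the entry limit is the lower of the two, so a patient can be eligible and already below the outcome rate. With no new-onset rule, that patient can be scored as an event that treatment had no chance to prevent. Such events, counted in both arms, shrink the difference between them. The trial is un-blinded (section 4.0), so leaving the start time and reference value to judgement also leaves room for classification that differs by arm.

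**Working it through.** **1. The unit.** The input is the 0.3 g/dl of 7.2 item 5a.

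- 0.3 g/dl × 1000 = 300 mg/dl.
- Against the entry limit in 5.2: 300 / 3 = 100 times.
- Against the top renal cut-off of the SOFA table in 2.5: 300 / 5 = 60 times.

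The SOFA table and the exclusion and re-entry limits in 5.2 (3 and 2.5 mg/dL) all use mg/dl.

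**2. What is lost without 5a.** A rise of 0.3 mg/dl is smaller than a 50% rise when 0.3 < 0.5 × baseline, that is, when baseline > 0.3 / 0.5 = 0.6 mg/dl. As a share of baseline, 0.3 mg/dl is 37.5% at 0.8, 30% at 1.0 and 15% at 2.0 mg/dl. Patients whose rise lies between 0.3 mg/dl and 50% of baseline count only if they meet 5c or need dialysis.

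**3. Entry limit against outcome threshold.** The inputs are 400 cc/24h (5.2), 0.5 ml/kg/hr (7.2 item 5c) and the 70 kg reference weight that section 6.2 uses for its fluid totals.

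- Outcome threshold as a volume: 0.5 × 70 × 24 = 840 mL/24h.
- Entry limit as a rate: 400 / 24 / 70 = 0.24 ml/kg/h (0.33 at 50 kg, 0.17 at 100 kg).
- Weight at which the two agree: 400 / (0.5 × 24) = 33.3 kg. Above it, the entry limit is below the outcome threshold.
- If the re-entry note is read as 400 cc passed in 12 hours: 400 / 12 / 70 = 0.476 ml/kg/h, still under 0.5.

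A 70 kg patient passing from 400 to just under 840 mL/24h is therefore eligible and already below the outcome rate.

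**4. Size of the dilution (illustration).** The documents give neither the prevalence of AKI at entry nor an expected AKI rate. Assume that new AKI is 40% (SC) vs 20% (SC + EMR) among patients free of it, and that a fraction q in each arm already has it. Counting everyone, the observed rate is q + (1 − q) × p, so the 20-point difference shrinks to (1 − q) × 20 points. Power is from the normal approximation for two proportions, two-sided 0.05. As a check, the same formula gives 0.902 for 70% vs 40% with 56 per arm, which agrees with the 90% in section 10.2.

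| q | Rates, everyone (56 per arm) | Power, everyone | AKI-free per arm (56 × (1 − q), rounded down) | Power, 40% vs 20% |
|---|---|---|---|---|
| 10% | 46% vs 28% | 51% | 50 | 59% |
| 20% | 52% vs 36% | 40% | 44 | 54% |
| 30% | 58% vs 44% | 32% | 39 | 49% |
| 40% | 64% vs 52% | 25% | 33 | 42% |

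Over this range the smaller denominator costs less power than the dilution does.

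**The case against.** **The unit corrects itself.** Item 5 cites a named external definition and the rest of the document uses mg/dl, so an analyst would probably recognise a slip. That is likely. But this is the working definition of an outcome, not background text, and no correct value appears elsewhere in the document.

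**Other criteria still work.** A reader might infer that creatinine-based AKI goes undetected, or that the outcome is void. The text does not support either. Criterion 5b is based on creatinine and usable, and 5c and dialysis also identify cases. Criterion 5b has no 48-hour window, so it can catch slower rises that 5a would not. The net number of cases lost is unknown. Nor does the unit error by itself pull the comparison toward no difference: a criterion missing equally in both arms lowers event counts and precision, but need not bias the risk ratio. The dilution argument belongs to the baseline gap alone.

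**The plan never says that entry oliguria counts.** A reader might infer that it is an outcome event by definition. Section 10.1 speaks of "incidence of acute kidney injury (dichotomous variable"), section 7.2 concerns prospective collection with day 0 as the day of recruitment, and secondary objective 3 is about reducing complications. All three point to new cases. A low 24-hour volume also does not itself document more than 6 hours of oliguria. This objection stands to the extent that the finding is a gap, not a stated rule. None of these phrases sets a rule, and the contrast with "Any newly documented hospital acquired infection(s" leaves the literal reading open.

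**The power figures are assumed, and the plan claims no power for AKI.** This is correct. Power stays below 60% on either method across the range shown. The table gives direction and rough size only.

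**Conclusion.** The unit in 7.2 item 5a is wrong as written, and this needs no assumption: 300 mg/dl cannot occur. Its effect is confined to patients with a baseline above 0.6 mg/dl whose rise is at least 0.3 mg/dl but under 50% and who meet no other criterion.

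The baseline gap holds in a limited form. Read literally, item 5 allows oliguria present before treatment to be scored as an event, and entry admits such patients at any weight above 33.3 kg. That conflicts with the label used in 10.1. The dilution depends on how many patients are affected, which the documents do not state. On the assumed rates, the loss of power from counting everyone runs from about 8 percentage points at 10% prevalence to about 17 at 40%.

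The outcome is distorted, not void. AKI is secondary, and the 28-day mortality endpoint and N = 112 do not depend on it. The definition should be corrected before AKI is analysed.

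**What to change.** 1. In 7.2 item 5a, change g/dl to mg/dl.
2. In 7.2 and 10.1, count AKI only when a criterion is first met after randomisation, with the baseline creatinine of 7.1 as reference for 5a and 5b.
3. Add baseline urine output in ml/kg/h to 7.1. The screening check in 5.2 is an absolute volume and cannot serve.
4. Report AKI among patients who do not already meet the oliguria criterion at randomisation.

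The cost is a smaller denominator for AKI and one more baseline item taken from the chart. No extra patients or blood draws are needed, since 7.2 already schedules creatinine every 4 to 8 hours.

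One limit remains. Section 7.1 defines baseline for venous tests as within 12 hours of randomisation and asks for no earlier creatinine, so a creatinine-based AKI that began before entry cannot be classified from the required data. For that reason the restriction in step 4 rests on oliguria. Adjusting for baseline status, or counting only worsening, would be acceptable alternatives if written down in advance.

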8.0 SAFETY ASSESSMENTS

8.1 Theoretical and potential adverse events

The study intervention is assessing an infusion containing products, which are normal components of the diet and are not toxic in themselves. Although this trial is expected to be very safe there are four main etiologies by which harm may occur in any of the groups:

- 1. Fluid overload**
- 2. Electrolyte disturbances**
- 3. Hyper/hypoglycemia**
- 4. Hypersensitivity reactions**

Such events are frequent in an ICU, and medical personnel are well trained and experienced to deal with these situations. This, combined with the very close monitoring provided by ICU means that a serious adverse reaction is thought to be exceedingly unlikely. All of the described scenarios already have ICU management protocols.

As the study is unblinded, attending physicians and care team members will be aware of the contents of the solutions being infused. Thus, if the study team is not available to advise, the care team should be able to make a decision based on clinical factors and may use their discretion to discontinue the intervention where necessary.

8.2 Management of anticipated adverse events

1. Fluid overload

This is considered to be very unlikely as sepsis and particularly septic shock are conditions where aggressive fluid resuscitation is recommended (30). The amount of fluid administered daily is considered to be relatively conservative. Furthermore, patients requiring renal replacement therapy will be excluded for further intervention, so harm from this intervention is highly unlikely.

There is no consensus or standard definition of fluid overload. We ask physicians to discontinue other fluids in preference to the EMR investigation fluids when possible. If there is severe fluid overload whereby the primary team finds it necessary to discontinue the fluid, then the patient will be withdrawn. It is not considered acceptable to slow the rate of the study solution – if this is felt to be essential, then the study solutions will be weaned and fluid management left to the care of the primary team.

2. Electrolyte abnormalities

a. Hyperkalemia (see appendix)

- i. Once potassium reaches ≥ 5 mmol/L EMR solution I (with potassium) has to be substituted with EMR solution II (without potassium) – EMR II has to continue despite hyperkalemia. EMR I has to replace EMR II once potassium levels reach ≤ 4 mmol/L
- ii. Potassium levels over ≥ 5.5 mmol/L have to be treated with standard ICU protocol. If EMR I is infused this has to be recorded as an adverse event and EMR I must be immediately replaced with EMR II

b. Hypokalemia ($K \leq 3$) (see appendix)

The ICU patients typically demonstrate low serum potassium level between 3 and 3.5, which are typically treated using the standard ICU electrolyte replacement protocol. Only serum potassium level of ≤ 3 will be reported as an adverse event.

c. Hypernatremia (Na >150)

- i. Discuss with study team – this may be criteria for cessation of intervention. Record as adverse event. If study team not immediately available (i.e. weekends, nights) wean infusion at discretion of attending responsible.
 - Caution with glucose once EMR is stopped – glucose management algorithm must continue to be followed.

d. Hyponatremia (Na <130)

- i. Additional sodium replacement (or diuresis) at discretion of primary team
- ii. If SIADH suspected and for fluid restriction – intervention has to be weaned. Caution with glucose once EMR is stopped(weaned) – glucose management algorithm must continue to be followed.

e. Severe Hypermagnesemia (Mg >4 mg/dl)

- i. Study intervention is to be stopped. Record as adverse event. Manage as per ICU protocol

f. Hypomagnesemia (Mg <1.5mg/dl)

- i. Replace as per ICU guidelines – N.B. target magnesium is ≥ 3 mg/dl in intervention group

g. Aluminum toxicity

- i. Aluminum toxicity is seen in neonates; however, this population is excluded in our study.

- ii. Patients in renal failure are at risk of bio-accumulating aluminum when solutions contain >50 micrograms/L. In this study, patients with renal failure are excluded and free amino acids only contains <25 micrograms/L.
- iii. Currently, to measure blood aluminum levels is not standard of care in a) patients not at risk of bio-cumulating the metal, b) patients receiving solutions that contain aluminum below 50 micrograms/L.
- iv. Aluminum toxicity is not an expected adverse event in this study patient population.

h. Hypophosphatemia (PO4 <1mg/dl)

- i. Additional replacement as per standard ICU guidelines

i. Hyperphosphatemia (PO4 >6.5mg/dL)

- i. Check renal function and calcium. Discuss with principal investigator. Hyperphosphatemia is not usually symptomatic and does not usually cause direct toxicity. The product of calcium x phosphate should be less or equal to 60. Record as adverse event

3. Hyper/hypoglycemia (see appendix)

For the very likely event of hyper/hypoglycemia in the EMR group we have developed an algorithm, which is a slight modification of standard ICU glucose management protocols and itself refers to ICU sliding scale insulin protocols. As glucose management is anticipated as a potential issue, monitoring of glucose is to occur at least hourly in the treatment arm. Please see appendix for detailed information on glucose management. Target glucose is 140-180mg/dl.

4. Allergic reactions (related to study components or suspected relation)

- Urticarial reaction
 - Begin antihistamine. Record as possible adverse event. Monitor patient – if EMR components suspected as the causative AND worsening reaction consider stopping solution and replace with D50 IV solution and exclude the patient from the protocol. At the same time treat the patient until reaction resolves. (Frequent glucose monitoring once solution discontinued). Contact principal investigator and follow hypersensitivity institutional protocol.
- Anaphylaxis
 - As mentioned above, if EMR causes an anaphylaxis reaction, begin emergency anaphylaxis management as per ICU protocol. Record serious adverse event and inform research team immediately. Stop solution and replace by D50 IV solution until a decision is made to exclude the patient from the protocol. At the same time treat the patient until reaction resolves. Caution with glucose once EMR is stopped – glucose management algorithm must continue to be followed. Contact study lead.

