1.0 STUDY OBJECTIVES

1.1 Primary Objective:

To assess the efficacy of administering Early Metabolic Resuscitation with Standard of Care (SC + EMR) in patients diagnosed with septic shock for reducing 28-day mortality versus using the Standard of Care alone (SC). Twenty-eight day mortality is defined during the time from the day SC+EMR or SC was first administered until a patient dies or is followed through 28 days (whichever comes first).

1.2 Secondary Objectives:

1. To assess whether Early Metabolic Resuscitation with standard of care (SC + EMR) is an effective strategy to reduce ICU mortality, hospital mortality, and 90-day mortality of septic shock patients relative to SC. ICU mortality is defined as mortality at ICU discharge relative to SC.
2. To compare the time to death from any cause between patients administered SC + EMR versus SC after being diagnosed with septic shock.
3. To assess whether SC + EMR is an effective strategy to reduce complications of septic shock such as: i) acute kidney injury, ii) dialysis requirements, iii) need for cardiovascular support or days on vasopressors, iv) need for invasive ventilation, days on ventilator support, v) duration of ICU stay, and vi) duration of hospital stay versus SC.
4. To describe the presence of any adverse effects between the two study groups (SC + EMR group vs SC group); thus, characterizing their safety.

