6.4 Adherence Assessment

Adherence will be defined as continuous infusion of study solutions 90% of the time from onset of study until cessation. This will be assessed via the electronic patient record, which will record infusion stop/start times.

Patients who have requested to be withdrawn from the study or achieve Comfort Care status during ICU stay will be removed from the study. Those who die or begin renal replacement will be followed up but the interventions will be stopped.

[figure not shown]

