9.0 CRITERIA FOR INTERVENTION DISCONTINUATION

These include:

- Patient's consent withdrawn
- Patient's discharge from the ICU
- Allergy to any of the components of EMR
- Patient requiring renal replacement therapy
- Patient's death
- Patient changed to Comfort Care status
- Patients receiving greater than 70% of their nutritional needs via enteral nutrition
- Unable to undergo placement of CVC for any technical reasons or withdrawal of CVC
- Severe fluid overload or electrolyte abnormality requiring discontinuation (as described in Chapter 7)
- Jehovah's Witness who decides not to accept albumin.
- If patient develops a known contraindication, or an unspecified condition where the clinician thinks the patient should be taken off the protocol, then there should be a discussion and treatment should be weaned according to safety protocol.

In case of discontinuation, please follow weaning procedure detailed in section 6.7.

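### Section 8.2 does not say what withdrawn or excluded patients leave; its triggers need study infusion, so read literally it can remove EMR patients only from follow-up and analysis.

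*Combined protocol and SAP*

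**What the plan says.** Section 8.2 uses patient-level removal wording in three places:

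- Fluid overload (item 1): "If there is severe fluid overload whereby the primary team finds it necessary to discontinue the fluid, then the patient will be withdrawn". It does not say from what. Two sentences later, where slowing the infusion is felt to be essential, it says "the study solutions will be weaned and fluid management left to the care of the primary team".
- Urticaria (item 4), where an EMR component is suspected and the reaction is worsening: "consider stopping solution and replace with D50 IV solution and exclude the patient from the protocol".
- Anaphylaxis caused by EMR (item 4): "Stop solution and replace by D50 IV solution until a decision is made to exclude the patient from the protocol".

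Other sections bear on what happens to these patients:

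- Section 9.0 lists allergy to an EMR component among the criteria for discontinuing the intervention, and also "Severe fluid overload or electrolyte abnormality requiring discontinuation (as described in Chapter 7"). That cross-reference misses, because the description is in section 8.2.
- Section 6.4 removes from the study patients who ask to withdraw or move to Comfort Care. Of others it says: "Those who die or begin renal replacement will be followed up but the interventions will be stopped". Overload and allergy appear in neither group.
- Section 7.2 (outcome data, item 8) follows all patients for up to 90 days.
- Section 10.3 mentions a full analysis set of 112 without defining it. Section 10.5 has no intention-to-treat statement and no rule for withdrawn patients.
- Section 1.2, objective 4, is "To describe the presence of any adverse effects between the two study groups (SC + EMR group vs SC group"). Section 8.3 limits adverse-event logging to 7 days from enrolment.

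**The concern.** Stopping the study fluid, or reacting to an EMR component, requires that EMR is running. No SC patient can meet these triggers. If withdrawal or exclusion is taken to mean leaving the study, patients can be lost after randomisation from one arm only, and because of harm.

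The decision is also open to judgement. The trial is unblinded, section 8.1 lets the care team stop the intervention at its discretion, and section 8.2 acknowledges that fluid overload has no standard definition.

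Two comparisons are exposed. For 28-day mortality, losing EMR patients who die more often than average lowers the apparent EMR death rate with no treatment effect. For objective 4, those patients would stop contributing adverse events for the rest of the 7-day window, while SC patients contribute throughout.

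**Working it through.** **1. Do the passages settle the meaning?**

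| Source | Points towards |
|---|---|
| 8.2: the patient is withdrawn, or excluded from the protocol | leaving the study |
| 8.2, electrolyte items: the intervention is weaned or stopped | treatment stop is worded differently when that is meant |
| 6.4: *withdrawn* used for leaving the study | leaving the study |
| 6.4: only death and renal replacement are stopped but followed | these patients are not covered |
| 8.2, item 1: study solutions weaned | stopping treatment |
| 9.0: overload and allergy end the intervention | stopping treatment |
| 7.2: all followed up to 90 days | staying in follow-up, though 6.4 itself makes exceptions |
| 10.3, 10.5 | silent |

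Both readings are available, and the analysis section does not choose between them.

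**2. Reproduce the design (section 10.2).** Inputs: 70% vs 40%, two-sided 0.05, 90% power, pooled proportion 0.55.

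n = [1.960·√(2·0.55·0.45) + 1.2816·√(0.7·0.3 + 0.4·0.6)]² / 0.30² = 55.7, so 56 per group as stated. Power at 56 is 90.2% (exact chi-square 89.6%).

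**3. Effect of dropping EMR patients when EMR does nothing.** SC is 56 patients at 70%, and true EMR mortality is 70%. Drop k of 56 EMR patients whose mortality is m:

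apparent EMR mortality = (56·0.70 − k·m) / (56 − k)

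For a share w the same formula is (0.70 − w·m) / (1 − w). The chance of a significant result favouring EMR comes from exact binomial enumeration of the two-sided, uncorrected chi-square test. Neither k (or w) nor m is in the documents; both are assumptions.

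| Dropped | m | Apparent EMR mortality | Spurious benefit (points) | Chance of false finding for EMR |
|---|---|---|---|---|
| none | – | 70.0% | 0 | 2.6% |
| 1 of 56 | 85% | 38.35/55 = 69.7% | 0.3 | 2.8% |
| 2 of 56 | 95% | 37.3/54 = 69.1% | 0.9 | 3.3% |
| 10% (50 kept) | 85% | 0.615/0.90 = 68.3% | 1.7 | 3.7% |
| 10% (50 kept) | 95% | 0.605/0.90 = 67.2% | 2.8 | 4.8% |
| 6 of 56 | 100% | 33.2/50 = 66.4% | 3.6 | 5.8% |
| any | 70% | 70.0% | 0 | about nominal |

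**4. Adverse-event window.** If logging stopped at withdrawal, and withdrawal came on average at mid-window (an assumption), the EMR arm would lose w × 0.5 of its observation time. That is 0.10 × 0.5 = 5% at w = 10%, and 2/56 × 0.5 = 1.8% for 2 of 56.

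**The case against.** The strongest reply is that 8.2 only stops treatment. It never says these patients leave the study, section 9.0 files the same events under intervention discontinuation, section 7.2 follows everyone, and where section 6.4 means removal from the study it says so. This stands as a reasonable reading, and perhaps the intended one. It does not close the gap: 6.4 omits these patients from its followed group, 7.2's *all* already has exceptions in 6.4, and nothing in 10.3 or 10.5 keeps them in the analysis.

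A reader might infer four stronger things, which the documents do not support:

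- *The plan removes these patients from the study.* It does not say so. The allergy exclusions are also not automatic: one is only to be considered, the other awaits a decision.
- *Only EMR patients can have the harm.* Section 8.1 places fluid overload and hypersensitivity in any of the groups. Only the removal trigger is specific to EMR.
- *The triggering events vanish.* Section 10.6 counts severe fluid overload and allergic reactions in the EMR safety rule, and 8.2 has the allergic events recorded. Only later events are at risk.
- *The bias could be large.* Dropping 25% at 85–95% mortality would give 7.9–14.0%. But 25% is section 10.6's limit for a composite that includes glucose and electrolyte events, which carry no such removal wording in 8.2. Section 8.2 calls fluid overload very unlikely.

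**Conclusion.** The point holds as an ambiguity that applies to one arm and that the analysis plan does not resolve. Followed literally, 8.2 can take patients out of the EMR arm alone, after an unblinded decision prompted by harm. The documents do not establish that this is intended or that it would happen often.

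Its size is unknown. With a few patients dropped, the effect on the primary test is small (2.6% to 2.8–3.3%). At 10% of the arm it is moderate (3.7–4.8%, a spurious benefit of 1.7–2.8 points). Both ranges assume no true effect and 85–95% mortality among those dropped. If those patients die at the arm's average rate, there is loss of information but no mortality bias. For adverse events, what could be lost is later events within the 7 days. If all 112 are analysed as randomised, the design is unaffected: 56 per group and 90.2% power.

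**What to change.** Reconcile 8.2 with 6.4, 7.2 and 9.0, limiting the change to follow-up and analysis:

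1. In 8.2, state that *withdrawn* and *excluded from the protocol* refer to the study infusion only.
2. In 8.2 or 6.4, state that these patients stay in follow-up, with adverse events logged for the full 7 days from enrolment and 28- and 90-day mortality collected.
3. In 10.5, state that all randomised patients are analysed in their assigned arm.
4. Correct section 9.0's reference to Chapter 7.

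Leave the clinical wording on when and how the infusion is stopped unchanged. The cost is a few sentences. Mortality follow-up to 90 days is already planned, and the sample size does not change. The small downside is a few more days of adverse-event logging for patients who are off the infusion.
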